9.2 Adverse Events and Serious Adverse Events

9.2.1 Adverse Events

An AE is defined as any undesirable physical, psychological, or behavioral effect experienced by a subject during his/her participation in an investigational study, in conjunction with the use of the drug, whether or not product-related. During the treatment of a migraine with study drug subjects will be asked if they are feeling anything unusual that they have not felt with a migraine before. A 'yes' response will trigger an alert to the site to contact the subject and assess the AE in terms of what the subject is experiencing, how long the symptoms lasted and how much the symptom(s) impacted them. During the time between dosing, subjects will be asked how they are feeling. A response of 'not well' will trigger an alert to the site to contact the subject and assess the AE similarly to the assessment of AEs reported during treatment. The occurrence of AEs should also be reviewed by non-directive questioning of the subject at each visit in the study. AEs may include, but are not limited to:

- Subjective or objective symptoms spontaneously offered by the subject and/or observed by the Investigator or medical staff, and

- Changes in laboratory abnormalities that are clinically relevant as assessed by the Investigator and for which a medical intervention was initiated.

Disease signs, symptoms, and/or laboratory abnormalities already existing prior to the use of the product are not considered AEs after treatment unless they reoccur after the subject has recovered from the pre-existing condition or, in the opinion of the Investigator; they represent a clinically significant exacerbation in intensity or frequency. AEs are collected from the time the subject signs the informed consent form until the completion of **EoS/ ET/Visit 6**. AEs reported prior to dosing will be captured and considered non-treatment emergent AEs. AEs reported 48 hours after dosing a migraine and between migraines will be captured and considered non-treatment emergent AEs.

All AEs must be recorded in the site's study records and the AE CRF with the following information:

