1. Relationship to Study Drug: The Investigator must assess whether they consider an AE to be drug-related. In assessing this relationship, the Investigator must use information about the drug as outlined in the Investigator's Brochure (IB), the subject's pre-existent medical conditions/concurrent medication, and chronology of the event relative to drug administration. The following definitions will be used:
 - **Reasonably or possibly related** applies to those AEs that, after careful medical consideration at the time they are evaluated, are considered by the Investigator (or other qualified physician) to have at least a possible relationship to study drug.
 - **Not reasonably or not possibly related** applies to those AEs that, after careful medical consideration at the time they are evaluated, are considered by the Investigator (or other qualified physician) to have no relationship, or no reasonable possibility of a relationship, to study drug.
2. Event Severity: The Investigator will be asked to assess the severity of the AE using the WHO Toxicity Criteria, as shown in Appendix 1. The WHO criteria assign a grade of 1 through 4 to indicate the severity of AEs. For AEs that are not listed in the WHO criteria, the Investigator will use medical judgment to assess the severity of the AE.

The following are guidelines to be used by the Investigator to judge the event severity of an AE that is not in the WHO Toxicity Criteria:

- Mild - awareness of sign or symptom, but easily tolerated
 - Moderate - discomfort enough to cause interference with usual activity
 - Severe - incapacitating with inability to work or perform usual activity
 - Life Threatening
3. Duration: Start and end dates and times, or if continuing.

4. Action taken.
5. Whether it constitutes a SAE, per definition below.
6. Outcome: resolved, resolved/ with sequelae, continuing, death, or unknown (only for subjects that are lost to follow-up).

The investigator (or designee) should attempt to establish a diagnosis of the AE based on the sign, symptoms and/or other clinical information. In such cases, the diagnosis, and not the individual signs/symptoms or laboratory abnormalities should be documents in the subject's source documentation and the CRF unless the etiology of the event is unknown. An assessment should be made at each visit (or more frequently if necessary) of any changes in severity, the suspected relationship to study drug, the interventions required to treat it and the outcome.

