### **12.1 Adverse Events**

An AE with the date of onset on or within 48 hours after a dose of study drug, or an event that worsens in intensity within 48 hours of a dose of study drug will be considered a treatment-emergent adverse event (TEAE). Other AEs are defined as those occurring after randomization but not considered to be treatment-emergent.

Descriptive statistics for both number of subjects ever experiencing an event as well as for the total number of events will be presented. Furthermore, descriptive statistics will also be calculated for each treatment group irrespective of first or second dose for AE relationship and AE severity. If multiple intensities are reported for a given AE and subject, then the most severe intensity will be counted. A separate, similar analysis will be conducted for TEAEs.

AEs with a missing start date will be assumed to be treatment-emergent, except in situations described in Appendix 1. If a subject takes at least one dose of study drug, but the date and time of dosing is missing in the e-diary, all AEs for that subject will be considered treatment-emergent, if the AEs occur between available date of dosing as recorded only in CRF for up to 48 hours (2 days) post recorded date of dosing. If the date and time of the second dose is missing in e-diary then all AEs for that subject will be considered as treatment emergent due to second dose, if AEs occur between available date of dosing in CRF for second dose, and an ending boundary of 2 days after recorded date of dosing with second dose, inclusive. See Appendix 1 for derivations related to partial dates and times.

Nausea and/or vomiting reported as adverse events during a migraine by any subject that also noted these as characteristics of their migraine will be presented by treatment groups and not be considered related to treatment but rather an underlying condition of the migraine.

AEs will be coded by the Medical Dictionary for Regulatory Activities (MedDRA) version 21.0.

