Unless otherwise stated, frequencies of adverse events will be displayed by applicable treatment group and overall. AEs will be sorted alphabetically by system organ class (SOC), preferred term (PT), and frequency. For the overall summary of AEs, both total subjects ever experiencing an event as well as total number of events will be presented. For all other summaries, subjects with multiple occurrences of the same AE preferred term will be counted once within the corresponding system organ class and preferred term.

Adverse events will be summarized by treatment arm in the following tables:

- Overall summary of AEs for Safety Population, 6-month, and 12-month population including:
  - All AEs
  - TEAEs
  - Other AEs
  - Related TEAEs
  - AEs leading to study discontinuation
  - Serious AEs
  - Related serious AEs
  - Deaths

- Incidence of All AEs and Other AEs by SOC for the Safety Population and Pre-administrative hold Population.
- Incidence of TEAEs by SOC for the Safety Population, 6 month and 12 month Safety Population.
- Incidence of TEAEs by decreasing frequency of PT for the Safety Population and Pre-administrative hold Population.
- Incidence of TEAEs occurring in more than 2% of subjects by quarter for Safety Population.
- Incidence of TEAEs and SAEs by SOC, PT and Doses for the Safety Population, 6-month and 12-month Safety Population.
- Summary of TEAEs by SOC, PT, and migraine attack sequence for the Safety Population.
- Summary of TEAEs by PT and migraine attack sequence for subjects that treated 5 or more migraine attacks in the Safety Population
- Summary of TEAEs occurring in more than 2% of subjects by PT for the Safety Population.
- Incidence of all SAEs by SOC for the Safety Population, 6 month and 12 month Safety Population.
- Incidence of All AEs leading to study discontinuation for Safety Population, 6-month and 12-month Population.
- Listing of All AEs leading to study discontinuation or death.
- Incidence of serious TEAEs for Safety Population, 6-month and 12-month Population. In addition, listings of these will be presented for Pre-Administrative Hold Population.
- Listing of Serious AEs.
- Time to onset and duration of TEAEs occurring in more than 2% of subjects relative to dosing regardless of second dose. If the time of adverse event is missing, no imputation will be performed for this presentation. The most frequent TEAE list will be finalized before interim soft lock and final database lock.

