#### **12.1.1 Relationship to Study Drug**

Summaries of AEs by relationship to study drug will classify AEs as either:

- Reasonably or Possibly Related
- Not Reasonably or Possibly Related

Related AEs are those that are recorded on the AE CRF page as “Reasonably or Possibly Related” or those with a missing relationship.

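### SAP Appendix 16.2 has no branch for AEs that worsen after a dose, against the TEAE definition in 12.1; secondarily, 12.1 and 12.1.1 give unreconciled rules on relatedness of nausea and vomiting

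*SAP*

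**What the plan says.** **Treatment emergence.** SAP 12.1 defines a TEAE in two limbs: onset at a dose or in the 48 hours after it, or an increase in intensity in that period. Protocol 10.5.1 has the same two limbs, and protocol 9.2.2 includes events present before dosing that exacerbate after the first dose. SAP 12.1 defines Other AEs as those after randomization that are not treatment-emergent.

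SAP Appendix 16.2 turns treatment emergence into an algorithm. It is headed as partial-date imputation, but it begins with rows for known start dates, including one where the stop date is also known. It uses start, stop and dose date/time only. A known start before the dose gives not TEAE.

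**Recording.** On worsening, protocol 9.2.1 says "An assessment should be made at each visit (or more frequently if necessary) of any changes in severity", without naming the record that holds the date of a change. The same section makes pre-existing conditions AEs if they recur after recovery or if "they represent a clinically significant exacerbation in intensity or frequency".

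**Relatedness.** SAP 12.1 takes nausea or vomiting reported as an AE during a migraine, in any subject who also noted it as a feature of their migraine, and says it will "not be considered related to treatment but rather an underlying condition of the migraine". SAP 12.1.1 states: "Related AEs are those that are recorded on the AE CRF page as" reasonably or possibly related, "or those with a missing relationship". It has no exception by symptom. Protocol 9.2.1 states: "The Investigator must assess whether they consider an AE to be drug-related".

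**The concern.** Safety is the primary objective, and SAP 3.1 names both TEAEs and other AEs in the primary safety endpoint. Dosing is intermittent over up to 12 months, so an AE that begins between attacks and is still present at the next dose is foreseeable. If such an event worsens after that dose, 12.1 counts it as a TEAE. The algorithm that a programmer would implement can send it to Other AEs instead. TEAE status also feeds the tables by organ class, quarter and attack sequence, the serious-TEAE tables, and the cardiovascular-risk comparison tested at 0.05.

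Relatedness is in neither primary endpoint. It does determine the related-TEAE row and the "Related serious AEs" row of the overall AE summary, and the summaries by relationship. The nausea and vomiting rule does not say whether the symptom must have been noted in that attack or at any time, does not name the source of that information, and sets no limit on onset, severity or seriousness. The diary records both symptoms only as present or absent (protocol 5.5.2 and 9.1.8). A rule driven by the diary could therefore not separate background nausea from nausea that intensified after dosing.

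**Working it through.** There is no stated figure to reproduce. The check sets the rules side by side.

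**1. Structure of Appendix 16.2.** Start date has 4 states: known; partial and unable to fall in the window; partial and possibly in the window; missing. Stop date has 3 states: known, partial, missing. 4 × 3 = 12 rows. Rows that mention worsening or intensity: 0.

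**2. Outcome for an AE that in fact began before the dose.**
- Known start (3 rows) and partial start that cannot fall in the window (3 rows): 3 + 3 = 6 rows give not TEAE, even if worsening is documented.
- The other 6 rows give TEAE when the stop is on or after the dose, or is missing. The result depends on the stop date, not on worsening.

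**3. Worked case.** Put the dose at hour 0. An AE after randomization starts at hour −24 and worsens at hour +6. Any earlier dose was before hour −24 − 48 = −72, so the AE was not already a TEAE from that dose.

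| Rule | Test | Result |
|---|---|---|
| SAP 12.1, protocol 10.5.1 | worsening at +6, within 0 to 48 | TEAE |
| Appendix 16.2, original start date kept | −24 < 0 | not TEAE, hence Other AE |
| Appendix 16.2, worsening entered as a new record starting at +6 | 0 ≤ 6 < 48 | TEAE |

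The conflict arises in the second line and disappears in the third. The documents do not say which recording convention applies, and the CRF is not part of them.

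**4. Who falls in the gap.** For a condition that existed before any use of the product, a clinically significant exacerbation is one of the things that makes it an AE under protocol 9.2.1, so that group is partly covered. What remains is an on-study AE as in step 3.

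**5. Relatedness.** Take a nausea AE during a migraine that the investigator marked as reasonably or possibly related, or left without an entry, in a subject who also noted nausea as a migraine feature. Under 12.1.1 it is related. Under 12.1 it is not. The 12.1 rule moves events only from related to not related.

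**6. Rows touched.** The overall AE summary in SAP 12.1 has 8 rows. The worsening gap touches 2 (TEAEs, Other AEs), or 3 if the event is related. The nausea and vomiting rule touches 2 (related TEAEs, related serious AEs). These counts locate the effect; they do not measure it.

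**7. Window edge (minor).** For a second dose dated only in the CRF, 12.1 runs from day 0 to day +2 inclusive, which is 3 calendar days. Appendix 16.2, with dates only, requires a start before dose date + 2 days: day 0 and day +1, which is 2 calendar days. With times available, an onset at exactly 48 hours is naturally read as inside the window in 12.1 and is outside it in 16.2.

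**The case against.** **On worsening.** The definition sits in the body of 12.1, which sends the reader to the appendix for missing and partial dates, so 16.2 could be meant to implement the onset limb only. That reading is weakened by the rows for known dates, which classify the event outright. The better objection is that a worsening may be entered as a new AE with its own start date, in which case the two rules agree. SAP 12.1 and protocol 10.5.1 foresee several intensities for one AE in one subject, which is compatible with separate records. This stands: the conflict is conditional on a convention that the documents do not give. A reader might infer that two programmers would necessarily classify such events differently, or that TEAEs will be undercounted. The documents support only that this could happen.

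**On relatedness.** A specific rule for two symptoms can be read as an intended exception to a general definition, and one cross-reference would settle precedence. The events remain presented by treatment group, and safety values are also listed. The in-attack prompt has subjects "asked if they are feeling anything unusual that they have not felt with a migraine before", so few nausea or vomiting events may meet the rule, and nothing shows that a serious one would. All of this stands and makes the point secondary. It does not remove it: neither section says which governs, the trigger is loosely scoped, and SAP 5.1 does not list the rule among its changes and clarifications. Events found through that prompt are ones the subject reported as new, which fits poorly with calling them the underlying condition.

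**Conclusion.** The main point holds as a defect in the text. Appendix 16.2, followed as written, omits the worsening limb of the TEAE definition and assigns the opposite result when the start is known to precede the dose. Its effect on classification rests on one assumption, that a worsened AE keeps its original start date. Under that assumption an event moves from TEAE to Other AE, both named in the SAP's primary safety endpoint.

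The relatedness point is real but secondary: an unstated precedence and an undefined trigger. Compared with 12.1.1, the rule in 12.1 can only lower the related rows.

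A reader might go further and conclude that the trial's overall safety result is altered. The documents do not support that. All-AE totals and the protocol's primary endpoint (any AE and specific AEs) are the same under every reading, and the nausea and vomiting rule leaves TEAE counts unchanged. The number of events affected cannot be computed, because no rates of worsening AEs or of migraine-associated nausea and vomiting AEs are given. This should be corrected, as a matter of clear and reproducible classification.

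**What to change.** 1. In Appendix 16.2, ahead of the not-TEAE outcome, add a branch: a start before a dose with intensity increasing within 48 hours after a dose is a TEAE. Name the record or field that dates the worsening, or state that a worsening is entered as a new AE record with its own start date.
2. Tabulate relatedness by the CRF entry under 12.1.1, with missing counted as related. Show the nausea and vomiting reclassification only in a labelled supplementary table, limited to attacks in which that symptom was recorded before dosing.
3. Minor: use a single 48-hour convention in 12.1 and 16.2, including for doses dated only in the CRF, and correct the reference in 12.1 from Appendix 1 to Appendix 16.2.

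The cost is a few lines of SAP text and a small programming change. With items 1 and 2, TEAE and related counts can only stay the same or rise, and Other AE counts can only stay the same or fall, by amounts that the documents do not allow to be estimated. The effect of item 3 depends on the convention chosen. SAP 5.6 plans the same outputs at the final lock as at the May 2018 lock, so the change should be recorded in SAP 5.1 to let the two sets of tables be reconciled.

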## **3 EFFICACY AND SAFETY ENDPOINTS**

### **3.1 Primary Safety Endpoint**

The proportion of subjects and the proportion of attacks associated with all adverse events and TEAE and other adverse events.

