## 5 GENERAL SPECIFICATIONS

This section details the specifications for summarizing all efficacy and safety endpoints.

All safety analyses will be based on the safety population. Efficacy analyses will be performed on ITT population, with the exception of the MBS-free and headache pain-free analyses secondary endpoint which will be performed on the mITT population.

Continuous variables will be summarized using descriptive statistics, i.e. n (number of subjects with available data), mean, median, standard deviation (SD), minimum, and maximum. For those measures that are analyzed using change from baseline scores, descriptive statistics will also be presented on observed scores, unless otherwise noted.

Minimum and maximum values will be presented to the same precision as the raw data. Mean and median will be presented to one more decimal place than the raw data. Standard deviation will be presented to two more decimal places than the raw data.

Categorical variables will be summarized using counts and percentages. Unless otherwise specified, percentages will be calculated using the numbers of subjects in the summarized population in each treatment group as denominators. Percentages will be presented with a precision of 1 digit after the decimal.

In this study, subject will enter the efficacy data on dosing and post-dose assessments in an e-diary. The e-diary records the date and time of the first dose and of the second dose and is programmed to assess specific time points and assessments as defined in the protocol based on the timing of the dose as recorded. This data is collected in the e-diary when e-diary is in migraine mode. Subjects will record the dosing information for every migraine attack in this study. Specifics of Migraine Mode are as below:

- Migraine Mode – First Dose
  - The e-diary enters Migraine Mode **ONLY** if the subject indicates taking his/her first dose of study medication
  - Post Dose Assessments will be completed using the Migraine Questions button at specific time intervals for up to 48 hours after the subject confirms taking study medication

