## **10 TREATMENT COMPLIANCE AND EXPOSURE**

Treatment compliance will not be calculated in the study.

Treatment exposure will be assessed in terms of the confirmed dose based on the CRF matched doses with subject's diary entered doses. Based on the matched CRF dosing dates, migraine numbers will be assigned for exposure analysis while still considering the 48 hour interval on the available data. Each treatment will be assigned a number to form a sequence. From the sequence, unique cluster IDs are assigned to treatments if a treatment belongs to an equivalence class of treatments intersecting within 48 hours of each other. Number of treatments will be limited to the maximum number of treatments a subject should have been able to take with respect to the 48 hour rule. This programming process will be used to determine the individual migraine attack. For unmatched CRF dosing dates (e.g. partial dates and dates falling out of visit windows), each reported dose will be counted as a separate migraine attack for safety and exposure analyses. This method will be applied by the programming team for validation purposes. Refer to the analysis dataset specifications for more details.

The number of subjects who have been treated with a first dose for the treatment of at least one migraine during the 0-3 month (Quarter 1) , 3-6 month (Quarter 2), 6-9 month (Quarter 3) and 9-12 month (Quarter 4) time intervals and similarly the number of subjects who have been treated with a second dose for at least 1 migraine during the 0-3 month (Quarter 1) , 3-6 month (Quarter 2), 6-9 month (Quarter 3) and 9-12 month (Quarter 4) time intervals will be reported.

Total number of doses for each subject during the entire study will be calculated based on the number of first and second doses for each treated migraine which will be same as total treated migraine attacks. This data will be calculated for individual subject's CRF confirmed dose data.

Subjects with at least 3 months, at least 6 months (6-Month safety population) and 12 months (12-Month safety population) in the study will be presented with average of  $\geq 2$  treated migraine attacks per month,  $\geq 3$  treated migraine attacks per month and  $\geq 4$  treated migraine attacks per month.

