Additionally, for safety population, 3-Month safety population, 6- Month safety population and 12-Month safety population, summary statistics for total number of treated migraine attacks will be tabulated. This data will be presented for n, mean, median, standard deviation, quartiles and minimum and maximum for each treatment group. Total number of treated migraine attacks will also be presented by each quarter as described previously in summary statistics for safety, 6-Month safety and 12-Month safety populations.

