- Subgroup analysis will be presented for subject with cardiovascular risk factors. TEAE will be compared among subjects with and without CVRF for individual event for Safety population. They will be tested with chi-squared test or fisher's exact test as appropriate with respect to sample size and all comparisons will be done at level of significance of 0.05.

Above tables will be presented for various types of AE criteria as below:

1. Incidence of TEAE table will be provided by-subject analysis. For this analysis, the adverse events will be reported out of total number of subjects in each treatment group regardless of whether a second dose is taken.
2. Similar events as Point #1 will be reported when only 1 dose was taken and additionally when 2 doses were taken.

3. Incidence of serious adverse events table will be reported by-subject analysis for each treatment group regardless of whether a second dose is taken.
4. Similarly, to Point # 2, serious events will be reported when only 1 dose was taken and additionally when 2 doses were taken.
5. TEAEs summary will be provided by each treated migraine analysis. For this analysis, the adverse events will be reported out of total number of treated migraines for each treatment group regardless of second dose.
6. Additionally TEAE by-subject analysis will be provided for treated 1st migraine attack, 2nd migraine attack, 3rd migraine attack, 4th migraine attack, 5th migraine attack, 10th migraine attack, 15th migraine attack, 20th migraine attack
7. Specific most common TEAEs will be reported in descriptive statistics (n, mean, median, SD, Minimum and maximum) by proportion of treated migraines attacks in subjects experiencing the TEAE at least once. This data will be presented out of total number of subjects in each treatment group. TEAEs will be reported if 2% or more of subjects any any treatment group report the event.

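### The by-quarter TEAE table has no stated denominator, and under the SAP default its percentages fall when fewer subjects treat, even if tolerability is unchanged

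*SAP*

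**What the plan says.** **By-quarter TEAE table.** SAP 12.1 lists "Incidence of TEAEs occurring in more than 2% of subjects by quarter for Safety Population". The entry names a population and no denominator. Two other rules supply one, and they agree:

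- SAP 5, unless otherwise specified: "percentages will be calculated using the numbers of subjects in the summarized population in each treatment group as denominators".
- SAP 12.1, item 1 of the numbered list, for by-subject TEAE incidence: "the adverse events will be reported out of total number of subjects in each treatment group regardless of whether a second dose is taken".

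The Safety Population (SAP 4) is every randomized subject who used at least one dose. Nothing requires the subject to be on study, or treating, in a given quarter. A TEAE is tied to dosing: "An AE with the date of onset on or within 48 hours after a dose of study drug", or worsening in that window (SAP 12.1).

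**Related plans.** Item 5 of the same list gives a per-attack summary: "the adverse events will be reported out of total number of treated migraines for each treatment group regardless of second dose". Item 6 gives by-subject TEAEs for selected attack numbers up to the 20th, with no denominator. SAP 10 reports, for each quarter, "The number of subjects who have been treated with a first dose for the treatment of at least one migraine during the 0-3 month" (and the later intervals), and adds: "Total number of treated migraine attacks will also be presented by each quarter".

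**Missing 2-hour ratings (separate).** SAP 11.1 presents pain-free response at 2 hours by 3-month period, counting an attack without a 2-hour rating as not pain-free. Protocol 10.6.2 promised a sensitivity analysis excluding missing data. SAP 5.1 drops it, on the grounds that the primary endpoint is safety and that missing diary data were examined in the parent study.

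**The concern.** The primary objective is the safety and tolerability of long-term intermittent use. A by-quarter TEAE table is where a reader will look to see whether tolerability changes over the year. If its denominator stays at the full arm while fewer subjects treat, the percentages drift down mechanically, and the drift looks like adaptation to the drug.

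The documents make a shrinking share plausible. Withdrawn subjects are not replaced (Protocol 6.4). Starting or changing migraine prophylaxis leads to withdrawal (Protocol 7.4). Subjects may be discontinued after more than a month with no treated attack (SAP 2.1). At the May 2018 lock (SAP 5.6), any subject not yet through the later quarters would have the same effect.

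The smaller point bears on the secondary objective, headache response over time. If the share of attacks without a 2-hour rating changes over the year, the missing-equals-failure rule moves the pain-free trend with it.

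**Working it through.** The plan gives no retention, TEAE or missing-rating figure, and its sample size rests on no hypothesis, so there is no stated number to reproduce. All rates below are assumed.

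**1. Effect of the default denominator.** For one arm and quarter, let N be Safety subjects in the arm, s the share who treat at least one attack, and r the TEAE rate among them. Subjects who treat nothing contribute essentially no TEAE; the exceptions are events soon after a dose just before the quarter boundary, or events with incomplete dates.

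Printed percentage = (N × s × r) / N = s × r. With treating subjects as denominator: (N × s × r) / (N × s) = r.

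With r = 20% in every quarter:
- s = 80%: 0.80 × 20 = 16%
- s = 65%: 0.65 × 20 = 13%
- s = 50%: 0.50 × 20 = 10%

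In counts: planned enrolment of about 2580 at 1:1 gives about 1290 per arm (assuming all are dosed). At s = 50%, 645 treat and 129 have a TEAE. 129/1290 = 10%; 129/645 = 20%.

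For a wider range, take r = 30% in all four quarters:
- s = 100/90/80/70%: prints 30/27/24/21%
- s = 100/75/60/50%: prints 30/22.5/18/15%
- s = 100/60/40/25%: prints 30/18/12/7.5%

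**2. Why changing the denominator is not enough.** By-subject incidence also depends on how many attacks each subject treats. Take a constant per-attack TEAE rate p = 5% and m treated attacks per subject per quarter. Six per quarter corresponds to the minimum average of 2 per month in SAP 2.2, which is a target for a subset and not expected use in the arm; the lower counts are assumed.

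- Independent attacks, 1 − (1 − p)^m: m = 6/5/4/3 gives 26.5/22.6/18.5/14.3%.
- Beta-binomial, within-subject correlation 0.3: 15.7/14.4/12.7/10.8%.
- Per-attack rate: 5% throughout.

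These figures do not measure the defect. They show why a per-attack rate by quarter should stand beside the by-subject figure.

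**3. Missing 2-hour ratings.** Printed pain-free = (rate among rated attacks) × (1 − missing share). With 30% among rated attacks:
- missing 2/4/6/8% by quarter: 29.4/28.8/28.2/27.6%, a false fall of 1.8 points
- the reverse order: a false rise of 1.8 points
- a constant 5%: 28.5% in every quarter, a lower level and no trend

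Each 1-point change in the missing share moves the figure by 0.3 points.

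**The case against.** **The plan already contains safeguards.** This is largely true. The attack-sequence table for subjects who treated 5 or more attacks is a fixed cohort over its first five attacks, so attrition cannot dilute it. TEAE tables are planned for the 6- and 12-month safety populations, which are defined by participation and dosing frequency. Frequency counts are shown with percentages, and SAP 10 gives subjects treated per quarter, so a reader could rebuild the right percentage if the quarter windows match. None of these sets the denominator of the by-quarter table, and the 6- and 12-month tables are not stated to be split by quarter.

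**The per-attack rate by quarter may already be planned.** The sentence introducing the numbered list in SAP 12.1 applies its items to the tables above it, and the by-quarter table is one of them. If item 1 reaches that table, item 5 may too. The introduction cannot be literal for every entry, since some are listings or SAE tables. Even if item 5 does apply, its stated denominator is all treated migraines in the arm, not those of the quarter. The text needs settling on either reading.

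**A reader might infer that the primary endpoint is biased.** The documents do not support this. SAP 3.1 defines it as "The proportion of subjects and the proportion of attacks associated with all adverse events and TEAE and other adverse events", with no time split. Only the secondary efficacy endpoint is defined per 3-month period.

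**The choice of denominator is partly preference.** Subjects on study in the quarter is an alternative. Subjects treating fits better because a TEAE requires a dose, and that count is already planned.

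**On missing ratings,** a reader might infer an undisclosed departure from the protocol. It is disclosed with a reason in SAP 5.1, a route Protocol 10 allows. The endpoint is descriptive, and Protocol 10.6.2 itself regards missing-as-failure as conservative. Attacks with no post-dose data are probably excluded already, since the protocol's mITT definition requires a post-dose assessment; the SAP's first-dose mITT definition cannot be seen in the text available. SAP 11.2.1.4 gives a partial observed-data view over the first three attacks. What remains is that a parent-study check does not address missingness that may change over 12 months of repeated attacks.

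**Conclusion.** The main point holds. As written, the by-quarter TEAE table divides by all Safety Population subjects in the arm, and its percentages fall in proportion to the share still treating. The direction needs only that fewer subjects treat in later quarters. The size (20% printing as 16%, 13% or 10% in the illustration) depends wholly on assumed inputs. The denominator is inferred from the general default and item 1, because no table shell is visible. The consequence is a possible misreading of one descriptive display that bears on long-term tolerability; the whole-study proportions are unaffected. It should be corrected because the remedy is cheap.

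The missing-rating point is real but of low severity. It affects the trend only if the missing share changes by quarter, and the documents do not say whether it does.

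**What to change.** **SAP 12.1.**
- State that the by-quarter TEAE denominator is Safety Population subjects in the arm who treated at least one attack in that quarter. Print that n, and use the same quarter windows for numerator and denominator.
- State that the item 5 per-attack TEAE rate is also given by quarter, with attacks treated in that quarter as denominator.
- State that the item 6 denominator is subjects who treated that numbered attack.

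**SAP 11.1 and 5.1 (lower priority).** Report the number and share of attacks without a 2-hour rating by quarter and arm. Restore the Protocol 10.6.2 check as an attack-level, by-quarter descriptive analysis that excludes those attacks and still counts attacks with rescue medication before 2 hours as failures. Keep missing-equals-failure as the main analysis. The by-quarter, attack-level form extends the protocol check, which is worded for subjects.

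**Cost.** A few SAP sentences and descriptive tables from data already collected; the subject and attack counts by quarter are already planned in SAP 10. Later-quarter by-subject TEAE percentages may look less favourable than under the default. Neither change removes selective dropout: subjects who tolerate the drug poorly may leave, and those still treating in later quarters are a selected group.
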